## COMMERCIAL PRODUCTION AND CLINICAL TRIAL OF NIPRIMUNE®

## **Executive Summary**

#### Introduction:

This project proposes upgrading the NIPRD-Drug Manufacturing Facility to a cGMP-compliant finished herbal medicine manufacturing facility, enabling industrial-scale production of NIPRIMUNE with potential to produce other solid dosage herbal products. NIPRIMUNE is a trademarked phytomedicine derived from *Andrographis paniculata*, with demonstrated immunomodulatory, antiviral, and anti-inflammatory benefits developed by National Institute of Pharmaceutical Research and Development (NIPRD).

## The project aims are to:

- a. Upgrade the NIPRD-Drug Manufacturing Facility to cGMP standards for industrial-scale production of NIPRIMUNE®.
- b. Optimize the extraction of NIPRIMUNE® the active ingredient and formulation processes for large scale industrial manufacture.
- c. Conduct Phase 1 clinical trials to evaluate the safety of NIPRIMUNE® as an immune booster.

## Expected Outcomes:

- a. A cGMP-compliant facility for manufacturing NIPRIMUNE® solid dosage form finished herbal medicines.
- b. Optimized large scale industrial extraction and formulation protocols for NIPRIMUNE® production that meet international quality standards using optimized cGMP compliant processes.
- c. Clinical safety data for NIPRIMUNE® as an immune-modulatory phytomedicine.

### Project Impact:

This project aligns with the growing demand for standardized herbal products and innovative solutions in the pharmaceutical industry. It promises to:

[figure not shown]
- a. Sustainable availability of high-quality, potent immunomodulatory phytomedicines that are safe and efficacious that will be beneficial in many emerging diseases.
- b. Contribute to the promotion of phyto-industrial development and phyto- research and development.
- c. Increased productivity and stimulation of phyto- economic investment.
- d. Align with [name] Hope Agenda and NASENI's objectives of driving economic impact and societal well-being.

The major activities will include developing and validating a standardized process for NIPRIMUNE® production, conducting pilot commercial production and distribution with stringent quality control, as well as undertake Phase 1 clinical trial to evaluate the safety and efficacy of the product. The project is estimated to cost one hundred and ninety three million eight hundred and eighty thousand naira only (₹193,880,000) and will be completed within 12 months.

#### Conclusion:

Ultimately, this project will position Nigeria as a hub for herbal medicine research and development, and production, which is sure to drive economic growth and improving healthcare outcomes. By

achieving these objectives, the project will make a lasting impact on the nation's pharmaceutical industry and contribute to the well-being of Nigerians.

Label on NIPRIMUNE® Secondary package

## **Background**

Medicinal plants have been used for centuries in Nigeria and globally to prevent and treat various diseases. Nigeria's rich biodiversity, with over 7,895 plant species, offers a vast array of natural remedies that have been harnessed by traditional healers and modern practitioners. The use of herbal medicines is gaining popularity worldwide, driven by growing recognition of their efficacy, safety, and cultural relevance.

The benefits of herbal medicines are multifaceted. They provide a natural and sustainable healthcare option, leveraging traditional knowledge and the country's rich biodiversity. This approach can lead to relief from chronic diseases, improved overall well-being, and promotion of holistic health. Additionally, herbal medicines have the potential to contribute to wealth creation and poverty reduction, making them an attractive option for many individuals and communities.

Globally, many people are turning to traditional medicine as a complementary or alternative approach to conventional healthcare. This shift is motivated by factors such as better tolerance and relief from chronic diseases, emerging new diseases due to climate change, and the desire to improve overall well-being and promote holistic health. As the world grapples with the challenges of emerging diseases, and chronic health conditions due climate change. The potential benefits of herbal medicines are becoming increasingly apparent.

The growing interest in herbal medicines reflects a broader recognition of the importance of traditional knowledge and natural remedies in modern healthcare. Similar to practices in India and China, Nigeria's rich cultural heritage and biodiversity offer a unique opportunity to harness the potential of herbal medicines. By exploring and developing these natural remedies, Nigeria can improve healthcare outcomes, promote economic growth, and preserve its cultural heritage.

One of the significant challenges in the production of herbal medicines is standardization, particularly in relation to extraction, formulation, and quality control protocols, as well as corroborating folk safety and efficacy claims. To address this challenge, our proposed research and development project aims to strengthen the NIPRD's facility for producing granules of water extracts from various medicinal plants, with NIPRIMUNE® serving as a prototype. We will utilize innovative optimized procedures and technology to ensure the production of high-quality herbal products.

NIPRIMUNE® is a phytomedicine developed by NIPRD through meticulous research and development efforts. It is derived from *Andrographis paniculata* and has been standardized and formulated using innovative techniques. NIPRIMUNE® is registered under the trademark and listed with NAFDAC, ensuring its authenticity and quality. This herbal medicine is designed as an immune booster that alleviates several health conditions, including antiviral, antibacterial, flu-like symptoms, diarrhea, fevers, inflammation, and high blood pressure, thereby promoting general well-being.

The goal of this project is to effect commercial production of NIPRIMUNE by upgrading NIPRD's drug manufacturing facility to a cGMP-compliant phyto-medicine factory and conduct Phase 1clinical trial to establish the clinical safety of the product.

The commercial development of NIPRIMUNE aligns ultimately with the Renewed Hope Agenda of [name] as well as the working objective NASENI as far as innovative research and development, entrepreneurship, sustainable healthcare options and wealth creation.

Funding this project will unlock the full potential of Nigeria's biodiversity and break the ice for sustainable healthcare and economic growth. We believe that this project will make a significant contribution to the development of the herbal medicine industry in Nigeria and improve the health and well-being of Nigerians. It is sure to offer a bright future and opportunity for innovation, entrepreneurship, and collaboration in Nigeria.

## **Objectives of project:**

- a. To establish a cGMP-compliant facility for the production and quality control of NIPRIMUNE®.
- b. To develop and validate a standardized cGMP-compliant process for industrial-scale NIPRIMUNE $^{\otimes}$  production.
- c. To conduct pilot commercial production and quality control of NIPRIMUNE®.
- d. Carry out phase 1 clinical trials to assure clinical safety.
- e. To facilitate commercial distribution of NIPRIMUNE® to pharmacies.

## **Significance**

The successful completion of this project will:

- a. Sustainable availability of a safe and effective immune booster in the face of new emerging diseases.
- b. Contribute to the growth of the herbal pharmaceutical industry in Nigeria and beyond.
- c. Provide a platform for the development of standardized herbal products with proven efficacy and safety.
- d. Enhance the utilization of medicinal plants and promote their potential therapeutic benefits.

## **Conceptual Framework**

The conceptual framework of this project is directed towards upgrading the NIPRD-Drug Manufacturing Facility also known as NIPRD —Pharmaceutical Company Limited (NIPCO-Ltd) ]to a cGMP-compliant facility for industrial-scale production of NIPRIMUNE, as well as the proof of safety by carrying out phase 1 clinical study. These goals are set to be achieved by:

- a. Upgrading the facility to meet cGMP standards for industrial-scale production of NIPRIMUNE.
- b. Optimizing the extraction and formulation processes for large-scale production of NIPRIMUNE.
- c. Implementing validated quality assurance protocols to ensure the product meets international standards.
- d. Conducting Phase 1 clinical trials to evaluate the safety and efficacy of NIPRIMUNE.
- e. Facilitating commercial distribution of NIPRIMUNE to pharmacies.

## **Hypothesis:**

## Null Hypothesis:

Industrial-scale production of NIPRIMUNE granules using a cGMP-compliant facility and phase 1 clinical trial will not significantly improve the quality, safety, and effectiveness of NIPRIMUNE, nor its market acceptability and penetration.

## Alternative Hypothesis:

Industrial-scale production of NIPRIMUNE granules using a cGMP-compliant facility and phase 1 clinical trial will significantly improve the quality, safety, and effectiveness of NIPRIMUNE, thereby enhancing its market acceptability and increasing its market penetration.

## **Expected Outcomes:**

- a. A cGMP-compliant herbal active ingredient extraction facility for industrial-scale production of NIPRIMUNE and other herbal granules
- b. Standardized NIPRIMUNE granules and other herbal products that meet international quality standards
- **c.** By conducting Phase 1 clinical trials of NIPRIMUNE will ensure:
  - a. Regulatory Approval by generating data to support regulatory approval and listing with NAFDAC.
  - b. Evidence-Based Medicine by providing scientific evidence for the safety and efficacy of NIPRIMUNE.
  - c. Increased Confidence by enhancing confidence in the use of NIPRIMUNE among healthcare professionals and patients.
  - d. Market Potential by increasing the potential for NIPRIMUNE to be marketed and sold globally.
- d. Increased capacity for research and development of herbal medicines
- e. Job creation and economic growth through the commercialization of herbal products

By establishing a facility for producing herbal granules, this project will contribute to the development of innovative and effective herbal products, promoting public health and well-being.

The successful completion of this research projected: Production and Clinical Trial of NIPRIMUNE achieve several far reaching benefits that will make a significant contribution to Nigeria's economic growth, healthcare outcomes, and cultural preservation.

## Some benefits of the NIPRIMUNE project:

- 1. Improved healthcare outcomes and overall well-being for Nigerians by preventing and treating diseases through enhanced immune systems.
- 2. Easy access to NIPRIMUNE as a standardized herbal product with proven efficacy and safety.
- 3. Creation of employment opportunities, thus boosting Nigeria's economic growth.
- 5. Advancement of research and development in the herbal pharmaceutical industry.
- 6. Development of standardized production and quality control processes and protocols.
- 7. Generation of valuable safety and efficacy data through Phase 1 clinical trials that will confer confidence in its integration into mainstream healthcare system.

- 8. Boosting the phyto-pharmaceutical industry's growth.
- 9. Increase in the acceptability and competitiveness of Nigerian herbal products globally.

## **Investigators and Environment**

The National Institute for Pharmaceutical Research and Development (NIPRD) is a Federal Government parastatal under the Federal Ministry of Health. NIPRD plays a pivotal role in advancing pharmaceutical research and development in Nigeria through its multifaceted activities.

NIPRD Pharmaceutical Company Limited (NIPCO): NIPRD operates a functional Drug Manufacturing Unit registered under the Corporate Affairs Commission (CAC) as NIPRD Pharmaceutical Company Limited (NIPCO). This unit collaborates closely with various technical departments within NIPRD through a Memorandum of Understanding (MOU) to carry out its businesses and research. The 5 technical departments in NIPRD are:

- i. Medicinal Plant and Traditional Medicine
- ii. Microbiology and Biotechnology
- iii. Pharmacology and Toxicology
- iv. Pharmaceutical Technology and Raw Materials Development
- v. Chemistry and Quality Control

NIPRD also have a state of the act herbarium and, botanical farms and gardens for nursing and planting medicinal plants under the department of Medicinal Plant and Traditional Medicine. It also has an animal house facility and a central laboratory facility.

**Accreditation and Certification of Laboratories:** The laboratories within the technical departments are ISO 9001:2015 certified, demonstrating their commitment to quality management systems. Additionally, they are accredited by the ANSI-ASQ National Accreditation Board (ANAB) for ISO 17025:2017, which attests to their technical competence in testing.

**NIPRD Research Clinic:** NIPRD also has an accredited Research Clinic, further enhancing its capacity for rigorous research and development in the pharmaceutical sector. This clinic serves as a healthcare center for the communities around NIPRD namely Karmo, Idu, Gwagwa and Deidei and plays a crucial role in conducting clinical trials and studies that contribute to the advancement of healthcare solutions.

#### cGMP protocols practiced in the NIPCO

NIPCO production facility is arranged in such a manner that will ensure the production of quality products by preventing mix-ups, and contamination in the processing, encapsulation, packaging, and quality control areas through measures such as:

- 1. Organized arrangement of the work area such that a seamless flow of activities in a progressive coordination of activities: Separate areas for different stages of production, such as raw material storage, processing, encapsulation, and packaging, to prevent cross-contamination.
- 2. A one-way flow of materials and personnel to prevent mix-ups and contamination.
- 3. Designated points for every operation to maintain a controlled environment: such as weighing, encapsulation and packaging.
- 4. All containers and equipment in contact with raw materials, intermediates and finished materials are of stainless steel surfaces to prevent corrosion and facilitate cleaning.
- 5. Continuous regular in-process checks during every batch production to ensure product quality and detect any deviations.
- 6. A quality control section independent of manufacturing staff interferences for testing and analysis of raw materials, intermediates, and finished products.
- 7. Qualified and trained personnel to carry out the various activities such as production, quality control tests and other sundry activities that related to quality assurance.
- 8. Regular cleaning and sanitization of equipment, machinery, and facilities to prevent contamination.
- 9. Standard operating procedures (SOPs) for cleaning and sanitization to ensure consistency.
- 10. A controlled area for packaging to prevent mix-ups and contamination.
- 11. Strict controls on labeling to ensure accurate product identification and information.
- 12. Slated regular training programs for personnel on GMP, quality control, and production procedures.
- 13. Strict gowning procedures to prevent contamination from personnel.
- 14. Availability of detailed batch records to track production, quality control, and packaging.
- 15. Availability of documents such as Drug master File (NIPRIMUNE DMF), Standard operating procedures (SOPs) for production and quality control activities.
- 16. Strict control over documentation to prevent errors and ensure traceability.

#### METHODOLOGY FOR NIPRIMUNE PRODUCTION

**Extraction Method (Maceration):** A. parnicula extraction process involves the authentication of the herb followed by transfer to the grinder to reduce the article size before transfer to maceration tank which is equipped with a stirrer. A predetermine quantity of water is introduced to the tank and maceration tank and temperature set to 60 °C. Maceration is carried out with continues stirring for 12 h.

The macerated mass is transfared to a sieving tank. The marc is collected and the residual solid waste is then transferred for waste disposal deposit.

The maceration tank decoction methods. Their products are refined through extraction, concentration, and granulation.

## **Spray Drying Process:**

Spray drying is a method used to convert liquid extracts into powders by rapidly drying the liquid droplets in a hot gas stream.

The inlet and outlet temperatures are set to produce optimal drying and yield of extract.

The dry extract are harvested from the spray dryer tank and collected into suitable waterproof bags weighed, labelled and placed API store.

## **Quality Control on Herbal Extract**:

The under listed tests are carried out on any batch extracted herbal active ingredient:

- i. Finger print
- ii. Heavy metal content
- iii. Moisture content
- iv. Pesticide content
- v. Aflatoxin
- vi. Shelf life determination

## **Production of NIPRIMUNE Capsules**

Using predetermined quantities of the herbal extract and excipients (starch and microcrystalline cellulose) following an predetermined formula.

The powders are appropriately mixed and encapsulated using an automatic capsulating machine. Gelatin capsule shell size 0; black and green shell.

## **Quality Control on NPRIMUNE Capsules**

The under listed tests are carried out on every finished batch of NIPRIMUNE:

- i. Organoleptic evaluation
- ii. Weight uniformity
- iii. Disintegration time
- iv. Dissolution
- v. Shelf life determination

#### Primary packaging

NIPRIMUN is packed:

- i. Blister pack x10 capsules, size zero.
- ii. Bulk plastic container with label x 60.

## Secondary package

Simple glossy paper box packaging labelled appropriately.

## **CLINICAL TRIAL PHASE 1**

**Title:** A Phase I, Randomized, Double-blind, Placebo-controlled, Single Ascending Dose and Multiple Ascending Dose Clinical Study to Assess the Safety, Tolerability and Pharmacokinetics of NIPRIMUNE in Healthy Adult Volunteers.

#### Introduction

This is a Phase I clinical study of NIPRIMUNE, the Investigational Medicinal Product (IMP). The current study is designed to evaluate the safety and tolerability and pharmacokinetics of single and multiple oral doses of the IMP NIPRIMUNE, in healthy volunteers.

This phase 1 clinical trial is being undertaken to determine the safety of NIPRIMUNE in healthy human participants. Physical well-being, including laboratory investigations, will be closely monitored and evaluated. The clinical trial will be carried out in NIPRD Research Clinic and other accredited laboratory. The use of appropriate health diary by the patients will be introduced in the study.

NIPRIMUNE is a phyto-medicine that has demonstrated positive outcomes during in vitro and in vivo studies with anti-inflammatory ,antiviral and strong immunomodulatory characteristics.

This clinical study is planned as a double blind, randomised, placebo-controlled, combined clinical study of two parts: Single Ascending Dose (SAD) and Multiple Ascending Dose (MAD) studies, respectively. Pharmacokinetic (PK) profile of the NIPRIMUNE, will also be assessed in both parts of the study. The safety, tolerability and pharmacokinetic data and results obtained from this study will determine the potentially efficacious doses of the IMP NIPRIMUNE in the subsequent efficacy studies.

Between each cohort, an interim analysis of PK, safety and tolerability will be performed. The available data will be evaluated by an independent Drug Safety Monitoring Board (DSMB). Once a dose level is judged to be safe, the DSMB will allow the escalation to the next cohort.

Both the Investigator and study participants will remain blinded to the treatment administered (drug or placebo) till the final results of the study are obtained.

DSMB will provide recommendations about stopping, modifying or continuing the study. Decision to escalate to next dose level/ Cohort, will be based on interim analysis of pharmacokinetic data, 36-hr post-dose, and 30-days post dose safety follow-up.

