## Parameters to be Evaluated in the NIPRIMUNE Phase 1 Clinical Trial

- 1. Demographic and Baseline Characteristics: Collecting data on participants' age, sex, weight, and medical history.
- 2. Vital Signs: Vital signs, such as blood pressure, heart rate, and temperature.
- 3. Laboratory Parameters: Laboratory tests, such as blood chemistry, hematology, and urinalysis will be carried out on volunteers.
- 4. Electrocardiogram (ECG): Cardiac function and rhythm.
- 5. Safety and Tolerability: Critical observation of adverse events (AEs) and serious adverse events (SAEs).
- 6. Pharmacokinetics (PK): Absorption, distribution, metabolism, and excretion (ADME) of NIPRIMUNE will determined using developed markers.
- 7. Maximum Tolerated Dose (MTD): The highest dose that can be safely administered will be determined.
- 8. Pharmacodynamics (PD): The general effect of NIPRIMUNE on the body.
- 9. Immunogenicity: Evaluating the immune response to NIPRIMUNE.

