## Ethical Approval, Consent, Confidentiality, and Withdrawal

Ethical approval will be obtained from the National Health Research Ethics Committee of Nigeria, Federal Ministry of Health (NHREC). Informed written consent and assent will be obtained from participants.

*Consent:* The evaluation procedure will be explained to each subject and a written consent will be signed or thumb-printed before enrollment for the evaluation. Subjects may withdraw voluntarily at any point of evaluation.

Adverse Events: Adverse events are any undesirable experiences or events, which occur during the study or during a reasonable time thereafter, whether or not considered related to administration of the drug. Serious Adverse Events

Serious adverse events should be reported within 24 to 48 hours. This will ensure that other investigators are promptly cautioned

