## **Response Outcome Measures**

## Current Primary Outcome Measures:

Determine the safety, tolerability, and dose-limiting toxicities of medication. Determine the safety, tolerability, and dose limiting toxicities of NIPRIMUNE Assessed by frequency and severity of adverse events(AEs), and changes in vital signs, 12-lead ECGs and laboratory assessments as compared to baseline [Time Frame: From the time the participant is administered the first dose through the final follow up clinic visit, for a total of 12weeks

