dosing	of volunteers.	Absorption, distribution, metabolism, and excretion (ADME) of NIPRIMUNE.	

	
 
Data on Maximum Tolerated Dose (MTD)
 
Pharmacodynamics (PD): The general effect of NIPRIMUNE on the body.
 
Immunogenicity: Evaluating the immune response to NIPRIMUNE.
 
	
Data Collection and analysis	Processed data available and are adequately stored.	10
Report writhing	Report for all activities compiled	11

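### The protocol promises dose-limiting toxicities and a maximum tolerated dose, but defines no DLT, fixes no escalate/repeat/stop criterion, and ties no serious event in a running cohort to a dosing pause

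*Protocol*

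**What the plan says.** **What is promised.** Under Current Primary Outcome Measures the aim is: "Determine the safety, tolerability, and dose-limiting toxicities of medication". The assessment is by frequency and severity of adverse events and "changes in vital signs, 12-lead ECGs and laboratory assessments as compared to baseline". The list of parameters to be evaluated has the MTD as item 7: "The highest dose that can be safely administered will be determined".

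**How escalation is decided.** The clinical trial Introduction provides an independent DSMB and an interim analysis between cohorts. It says "Once a dose level is judged to be safe, the DSMB will allow the escalation to the next cohort". The decision "will be based on interim analysis of pharmacokinetic data, 36-hr post-dose, and 30-days post dose safety follow-up". The same section adds: "DSMB will provide recommendations about stopping, modifying or continuing the study".

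**Cohorts.** Arms and Interventions sets five single-dose (SAD) and two multiple-dose (MAD) cohorts of eight, each with six on active product and two on placebo. It allows extra volunteers for a repeated cohort, without saying when a repeat is needed.

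**Events within a cohort.** The section on ethics, consent and withdrawal says: "Serious adverse events should be reported within 24 to 48 hours". The stated purpose is that other investigators are cautioned promptly.

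**The concern.** The protocol says who decides on escalation (the DSMB), when (between cohorts) and on which data (PK, 36-hour and 30-day safety). It does not say what result leads to escalating, repeating or stopping.

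Two things are at stake. The first is the safety of healthy volunteers: nothing obliges the site to stop dosing the rest of a cohort after a related SAE. The second is interpretation: the same cohort data could lead to any of the three decisions, so the MTD would rest on a criterion chosen after the data are seen, and the DLT part of the primary outcome cannot be scored as written.

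A pause rule binds site staff during dosing and a DLT definition drives dose decisions. Both therefore belong in the protocol and would not normally be left to a SAP.

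**Working it through.** **1. Design figures.** 5 × 8 + 2 × 8 = 56 volunteers, which matches the stated total. Active: 7 × 6 = 42. Placebo: 7 × 2 = 14.

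**2. What the text fixes and what it leaves open.**

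| Element | Stated | Not stated |
|---|---|---|
| DLT | Domains assessed: adverse events, vital signs, ECG, laboratory | Qualifying event, threshold, attribution, observation window |
| Outcome table | Related SAEs, discontinuations, markedly abnormal findings | The markedly abnormal limits; any link to DLT or escalation |
| Escalation | DSMB judgement on PK, 36-hour and 30-day data | The result that permits it |
| Repeat | Foreseen | When |
| Stop | DSMB may recommend it | Any finding that requires it |
| SAE report | 24 to 48 hours | Pause, or review by the DSMB |

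**3. The within-cohort gap in MAD.** Pre-dose sampling on Days 2–6 and a final dose on Day 7 imply daily dosing over seven days. Assume that the cohort starts together. A related SAE on Day 2, reported at the 48-hour limit, is known on Day 4. The other volunteers still have doses on Days 5, 6 and 7, and the report does not require anyone to withhold them.

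**4. How much the unwritten criterion matters (illustration).** The protocol gives no DLT rate, so the rates p are assumed. With six active volunteers and k events tolerated:

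P(goes forward) = Σ (i = 0 to k) C(6,i) pⁱ (1 − p)⁶⁻ⁱ

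At p = 0.20: k = 0 gives 0.8⁶ = 0.262; k = 1 adds 6 × 0.2 × 0.8⁵ = 0.393, giving 0.655; k = 2 adds 15 × 0.2² × 0.8⁴ = 0.246, giving 0.901.

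| Assumed rate | k = 0 | k = 1 | k = 2 |
|---|---|---|---|
| 10% | 0.531 | 0.886 | 0.984 |
| 20% | 0.262 | 0.655 | 0.901 |
| 1/3 | 0.088 | 0.351 | 0.680 |

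Even with no events in six, the one-sided 95% upper limit for the rate is 1 − 0.05^(1/6) = 0.393.

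**5. Two possible rules with a repeat (illustration).** Both count DLTs in the six active volunteers, and a repeated cohort passes only if its new six have none.

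- Strict (0 escalate, 1 repeat, 2 or more stop): P(pass) = P(0) + P(1) × P(0).
- Less strict (0–1 escalate, 2 repeat, 3 or more stop): P(pass) = P(0) + P(1) + P(2) × P(0).

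At 5%, P(0) = 0.735, P(1) = 0.232 and P(2) = 0.031. Strict: 0.735 + 0.232 × 0.735 = 0.906. Less strict: 0.735 + 0.232 + 0.031 × 0.735 = 0.990. At 20% the figures are 0.365 and 0.720. All five SAD cohorts at a constant 5%: 0.9057⁵ = 0.610 against 0.9897⁵ = 0.949. A constant rate over ascending doses is a simplification.

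**The case against.** The strongest reply is that the protocol does have safeguards. The DSMB is independent, its remit to recommend stopping is not confined to the between-cohort reviews, and 30 days of follow-up precede every escalation. That stands, and it lowers the risk. It supplies neither a criterion nor a trigger, and nothing requires the SAE report to reach the DSMB.

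The MTD is also less central than a reader might think. The title and purpose are safety, tolerability and PK, and the primary outcome table lists neither DLTs nor the MTD. The MTD entry in the project activities table adds little, because that table describes a single-blind study in 25 volunteers, at odds with the main design. Still, the narrative primary outcome and the parameter list are enough to create the obligation.

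A DSMB charter might hold the rules. The protocol mentions none, and site staff would need the pause trigger in the protocol in any case.

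A reader might infer that the protocol directs dosing to continue after a related SAE. It does not; it is silent, and the investigator or DSMB could stop. A reader might also take the percentages as the risk in this trial. They are not: the rates are assumed, and the DSMB would weigh PK, placebo data and clinical detail, not a count alone.

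**Conclusion.** The point holds and should be settled before the first volunteer is dosed. In the text available, no DLT is defined, no finding is tied to escalating, repeating or stopping, and an SAE in a running cohort triggers neither a pause nor a DSMB review. This rests on the wording and does not depend on any assumed rate.

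The exposure is greatest in the two MAD cohorts. In SAD, the protocol does not say whether the eight volunteers are dosed together; if they are, a pause has nobody left to protect in that cohort.

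The illustration shows only that the choice matters: at an assumed 20% rate, the chance of going forward runs from 26% to 90%. It does not identify a correct count. The strict rule in the working may cap the MTD too early, the looser one passes more toxic doses, and neither is safe if a related SAE is merely one event in the count. The number is a judgement for the sponsor and the DSMB.

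**What to change.** Amend the protocol before the first cohort.

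1. **Related SAE (Introduction and the SAE reporting text).** Any related SAE, on its own, pauses all dosing in the running cohort and all escalation. It goes to the DSMB within the 24 to 48 hour window, and dosing resumes only after the DSMB agrees. Keep this separate from any DLT count.
2. **SAD.** Where a cohort is not all dosed at one time, apply the pause to those not yet dosed. Without staggered dosing, the pause protects mainly MAD volunteers and later cohorts.
3. **DLT definition.** Build it from the outcome table: discontinuation for a related adverse event, or a treatment-related markedly abnormal laboratory, vital-sign or ECG finding, with thresholds and observation window stated. Add any related SAE.
4. **One rule.** The sponsor and DSMB fix a single escalate/repeat/stop rule in the six active volunteers, under which a dose with a related SAE is neither escalated nor repeated by count alone. The DSMB keeps its power to be more cautious. Define the MTD from that rule, and report it as not reached if no dose meets the stopping criterion.

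**Cost.** An amendment, occasional pauses, and someone outside the blinded team to give the DSMB the allocation. The DSMB is already named and has a budget line. The frequency of SAE pauses cannot be sized, because no SAE rate is given. Each repeated cohort adds eight volunteers and another 30-day wait; at an assumed 5% DLT rate that happens in 23% of cohorts under the strict illustration and 3% under the less strict one.
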